Investigator assessment of clinical response				X	X	X	The investigator will provide an assessment of clinical response (clinical success, clinical failure, or indeterminate, per the definitions in Section 10.11) for each participant at the TOC and Follow-up Visits, and at early withdrawal (if applicable). This assessment should be completed after the clinical signs and symptoms score is determined by the same study physician or otherwise appropriately medically trained staff who performed the clinical scoring assessment.
CCI							
Labs & blood/urine sampling							
Bacteriology samples	X		X	X	X	X	
 Participants will provide a clean-catch midstream urine sample at each visit for Gram stain, quantitative bacteriology culture, and in vitro antimicrobial susceptibility testing by a designated central laboratory(ies). Refer to the laboratory manual. A predose bacteriology urine sample will be collected at the On-therapy Visit.
Hematology, chemistry, and urinalysis	X		X	X			
Diagnosis of presumptive acute uncomplicated cystitis	X						Based on confirmation of nitrite or pyuria (>15 WBC/HPF or the presence of 3+/large leukocyte esterase) from a pretreatment clean-catch midstream urine sample per local laboratory procedures.
Urine pregnancy test	X		X	X		X	For women of childbearing potential, a negative high sensitivity urine pregnancy test is sufficient for eligibility. See Section 8.2.5 for Baseline urine test sensitivity requirements and 10.4 for associated contraception requirements. Pregnancy testing should

Visit	Baseline		On-Therapy ^a	TOC ^b	Follow-up	Early Withdrawal	Notes
Study Day	1		2 to 4	10 to 13	28±3	NA	be performed after Dose 4 and before Dose 8, as specified in Section 8.2.5.
Procedure	Pre-dose	Post-dose					
Serology (hepatitis B and C and HIV)	X						If serology testing was performed within 3 months prior to the first dose of study treatment and the results were positive, testing at Baseline is not required. If testing was performed within 3 months and any result was negative, testing at Baseline is required.
Drug and alcohol screen	X						
Genetic sample	X						Collect sample only if the participant has a signed consent/assent specific for this purpose. The Baseline Visit is the recommended time to collect the sample, but it can be collected at any time during the study.

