	A substantial increase in Cmax and AUC and decrease in clearance was observed in volunteer participants with severe hepatic impairment.	
Renal Effects In preclinical trials, mild to moderate tubular degeneration was noted in the rat and proteinuria in the dog. Proteinuria was also observed in humans.	No clinical evidence of renal toxicity has been seen in clinical trials to date. A substantial increase in Cmax and AUC and decrease in clearance was observed in severe renal impairment/ESRD participants not on hemodialysis and in ESRD participants requiring hemodialysis (note: gepotidacin may have been administered at any time other than when receiving dialysis).	Participants with severe renal impairment/ESRD (including those who may require dialysis) are excluded from Phase III trials. See Section 5.2 for excluded medical conditions. Monitoring criteria have been implemented.
Reproductive System Effects Preclinical studies demonstrated that gepotidacin was not genotoxic and no drug related malformations were observed. Although positive in vitro findings for clastogenicity, consistent with a mechanism related to mammalian topoisomerase II inhibition were found, in vivo data from rat micronucleus and COMET assays suggest that gepotidacin does not pose a genotoxic hazard to humans. Gepotidacin effects on embryofetal development were limited to decreased fetal weights for male and female fetuses in rats and decreased fetal weights and increased fetal resorptions (fetal deaths) in mice, both at maternally toxic doses. These occurred at clinically relevant exposure (65 µg.h/mL in rat and 35µg.h/mL in mouse).	There are no data on the use of gepotidacin in pregnant women.	Gepotidacin is not recommended in pregnant or nursing mothers. Pregnancy testing requirements in this study minimize the risk of exposure to a fetus. See 10.4 for contraceptive measures and Section 8.2.5 for required pregnancy testing.
Other		
Nitrofurantoin	The most frequent AEs possibly or probably related to oral nitrofurantoin treatment are nausea (8%),	Close monitoring of clinical parameters and AEs (Section 1.3) will be conducted, and treatment

Potential Risk of Clinical Significance	Summary of Data/Rationale for Risk	Mitigation Strategy

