9.3.4. Safety Analysis

All safety analyses will be performed on the Safety Population. All reported AEs will be coded using MedDRA and summarized by system organ class and preferred terms.

The safety estimand will use a treatment policy strategy for the ICE of study treatment discontinuation, as safety will be assessed at all post-baseline assessments irrespective of whether the participant completed the treatment.

Treatment-emergent AE (TEAE) is defined if AE onset date/time is on or after treatment start date/time. The number and proportion of treatment-emergent AEs, study treatment-related AEs, deaths, SAEs, and AEs leading to study treatment or study withdrawal will be provided. Treatment-emergent AEs will be summarized by maximum intensity.

Adverse events of special interest will include CV, gastrointestinal, and *Clostridiooides difficile infection or colitis* events. In addition, AEs associated with acetylcholinesterase inhibition are also considered special interest. As described in the SAP, manual and programmatic reviews of AEs/preferred terms will be used to assess these events.

The severity of specified AEs and laboratory abnormalities will be graded according to the modified DMID toxicity grading system (Section 10.12). Data will be tabulated and reported by absolute grade for Grades 3 and higher, and shift tables, as appropriate.

Change from baseline over time in laboratory parameters, ECGs and vital signs will be summarized with descriptive statistics. The frequency of laboratory abnormality events along with the shift from baseline to the worst-case post-baseline value will be provided. Abnormal liver chemistry results will be determined using increases above the upper limit of normal.

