10.2. Appendix 2: Clinical Laboratory Tests

- The tests detailed in [Table 16](#) except where indicated will be performed by the central laboratory.
- Local laboratory results are only required in the event that the central laboratory results are not available in time for either study intervention administration and/or response evaluation. If a local sample is required, it is important that the sample for central analysis is obtained at the same time. Additionally, if the local laboratory results are used to make either a study intervention decision or response evaluation, the results must be recorded.
- Protocol-specific requirements for inclusion or exclusion of participants are detailed in Section [5](#) of the protocol.
- Additional tests may be performed at any time during the study as determined necessary by the investigator or required by local regulations.

Table 16 Protocol-required Safety Laboratory Tests

Laboratory Assessments	Parameters						
Hematology	Platelet count	RBC Indices: MCV MCH		WBC count with differential: Neutrophils Lymphocytes Monocytes Eosinophils Basophils			
	RBC count						
	Hemoglobin						
	Hematocrit						
Clinical Chemistry ¹	BUN	Potassium	AST/SGOT		Total and direct bilirubin		
	Creatinine and creatinine clearance	Sodium	ALT/SGPT		Total protein		
	Glucose (non-fasting)	Calcium	Alkaline phosphatase		Albumin		
	Chloride	Magnesium	Phosphorus				
Routine Urinalysis	
 Specific gravity pH, glucose, protein, blood, ketones, nitrite, and leukocyte esterase by dipstick Microscopic examination (if blood or protein is abnormal) 						
Pregnancy testing	
 Urine human chorionic gonadotropin (hCG) pregnancy test (as needed for women of childbearing potential)² 
Note: See Section 8.2.5 for pregnancy test sensitivity requirements and additional pregnancy testing details.
						

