Other Screening Tests	
 • Serum or urine alcohol and drug screen (to include at minimum: amphetamines, barbiturates, cocaine, opiates, cannabinoids and benzodiazepines) • Serology [HIV antibody, hepatitis B surface antigen (HBsAg), and hepatitis C virus antibody]. If serology testing was performed within 3 months prior to the first dose of study intervention and results were positive, testing at Baseline is not required. If testing was performed within 3 months and any result was negative, testing at Baseline is required. • All study-required laboratory tests will be performed by a central laboratory, with the exception of dipstick urinalysis and urine pregnancy tests which will be performed locally.
-----------------------	---

ALT=alanine aminotransferase; AST=aspartate aminotransferase; BUN= blood urea nitrogen; HBsAg=hepatitis B surface antigen; hCG=human chorionic gonadotropin; HIV=human immunodeficiency virus; MCH=mean corpuscular hemoglobin; MCV=mean corpuscular volume; RBC=red blood cell; SGOT=serum glutamic-oxaloacetic transaminase; SGPT=serum glutamic-pyruvic transaminase; WBC=white blood cell.

NOTES :

1. Details of liver chemistry stopping criteria and required actions and follow-up assessments after liver stopping or monitoring event are given in Section 7.1.1 and Section 10.6 All events of ALT $\geq 3 \times$ upper limit of normal (ULN) and total bilirubin $\geq 2 \times$ ULN ($>35\%$ direct bilirubin) or ALT $\geq 3 \times$ ULN and international normalized ratio (INR) >1.5 , if INR measured, which may indicate severe liver injury (possible Hy's law), must be reported to GSK in an expedited manner (excluding studies of hepatic impairment or cirrhosis).
2. Local urine testing will be standard for the protocol unless serum testing is required by IRB/IEC.

Investigators must document their review of each laboratory safety report.

Laboratory results that could unblind the study will not be reported to study sites or other blinded personnel until the study has been unblinded.

10.3. Appendix 3: AEs and SAEs: Definitions and Procedures for Recording, Evaluating, Follow-up, and Reporting

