Alkaline Phosphatase	1.1 to <2.0 x ULN	2.0 to <3.0 x ULN	3.0 to 8.0 x ULN	>8.0 x ULN
Amylase	1.1 to 1.5 x ULN	1.6 to 2.0 x ULN	2.1 to 5.0 x ULN	>5.1 x ULN
Lipase	1.1 to 1.5 x ULN	1.6 to 2.0 x ULN	2.1 to 5.0 x ULN	>5.1 x ULN

ULN = upper limit of normal.

URINALYSIS				
	Grade 1	Grade 2	Grade 3	Grade 4
Proteinuria	1+ or 200 mg to 1 g loss/day	2 to 3+ or 1 to 2 g loss/day	4+ or 2 to 3.5 g loss/day	Nephrotic syndrome or >3.5 g loss/day
Hematuria	Microscopic only <10 RBC/HPF	Gross, no clots >10 RBC/HPF	Gross, with or without clots, or red blood cells casts	Obstructive or required transfusion

HPF = high-power field; RBC = red blood cells.

CARDIOVASCULAR				
	Grade 1	Grade 2	Grade 3	Grade 4
Cardiac rhythm	N/A	Asymptomatic, transient signs, no Rx required	Recurrent/persistent; symptomatic Rx required	Unstable dysrhythmia; hospitalization and treatment required
Hypertension	Transient increase >20 mm/Hg; no treatment	Recurrent, chronic increase >20 mm/Hg; treatment required	Acute treatment required; outpatient treatment or hospitalization possible	End organ damage or hospitalization required
Hypotension	Transient orthostatic hypotension with heart rate increased by <20 beat/min or decreased by <10 mmHg systolic BP. No treatment required	Symptoms due to orthostatic hypotension or BP decreased by <20 mmHg systolic; correctable with oral fluid treatment	Requires IV fluids; no hospitalization required	Mean arterial pressure <60 mmHg or end organ damage or shock; requires hospitalization and vasopressor treatment
Pericarditis	Minimal effusion	Mild/moderate asymptomatic effusion, no treatment	Symptomatic effusion; pain; ECG changes	Tamponade; pericardiocentesis or surgery required
Hemorrhage, Blood Loss	Microscopic/occult	Mild, no transfusion	Gross blood loss; 1 to 2 units transfused	Massive blood loss; >3 units transfused

BP = blood pressure; mmHg = millimetre of mercury; IV = intravenous; ECG = electrocardiogram; N/A = not applicable; Rx = therapy.

RESPIRATORY				
	Grade 1	Grade 2	Grade 3	Grade 4
Cough	Transient; no treatment	Persistent cough; treatment responsive	Paroxysmal cough; uncontrolled with treatment	N/A
Bronchospasm, Acute	Transient; no treatment; FEV1 70 to 80% of peak flow	Requires treatment; normalizes with bronchodilator; FEV1 50 to 70% of peak flow	No normalization with bronchodilator; FEV1 25 to 50% of peak flow; or retractions present	Cyanosis; FEV1 <25% of peak flow; or intubation necessary

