- ALT  $\geq$  8xULN
- ALT  $\geq$  5xULN
- ALT  $\geq$  3xULN
- AST  $\geq$  20xULN
- AST  $\geq$  10xULN
- AST  $\geq$  8xULN
- AST  $\geq$  5xULN
- AST  $\geq$  3xULN

- Total Bilirubin > 2xULN
- Total Bilirubin > 1.5xULN
- Total Bilirubin > 2xULN and a portion of Direct Bilirubin  $\geq 35\%$  on the same day
- Total Bilirubin > 1.5xULN and a portion of Direct Bilirubin  $\geq 35\%$  on the same day

\*: The total Bilirubin elevation must occur on or up to 28 days after the ALT elevation

\*\*: sign of hepatocellular injury, ALT and ALP values must occur on the same day.

Urinalysis results will be summarized using descriptive statistics. The severity of renal impairment will be evaluated and summarized according to the method in Section [6.2.2.2](#).

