## CONFIDENTIAL

214144

ENZYMES						
	Laboratory parameter	Display label	Grade 1	Grade 2	Grade 3	Grade 4
Aspartate aminotransferase (AST)	Aspartate aminotransferase	Aspartate aminotransferase (High)	1.1 to <2.0 × ULN	2.0 to <3.0 × ULN	3.0 to 8.0 × ULN	>8.0 × ULN
Alanine aminotransferase (ALT)	Alanine aminotransferase	Alanine aminotransferase (High)	1.1 to <2.0 × ULN	2.0 to <3.0 × ULN	3.0 to 8.0 × ULN	>8.0 × ULN
Gamma to glutamyl transferase (GGT)	NA	NA	1.1 to <2.0 × ULN	2.0 to <3.0 × ULN	3.0 to 8.0 × ULN	>8.0 × ULN
Alkaline Phosphatase	Alkaline Phosphatase	Alkaline Phosphatase (High)	1.1 to <2.0 × ULN	2.0 to <3.0 × ULN	3.0 to 8.0 × ULN	>8.0 × ULN
Amylase	NA	NA	1.1 to 1.5 × ULN	1.6 to 2.0 × ULN	2.1 to 5.0 × ULN	>5.1 × ULN
Lipase	NA	NA	1.1 to 1.5 × ULN	1.6 to 2.0 × ULN	2.1 to 5.0 × ULN	>5.1 × ULN

ULN=upper limit of normal.

URINALYSIS						
	Laboratory parameter	Display label	Grade 1	Grade 2	Grade 3	Grade 4
Proteinuria	NA	NA	1+ or 200 mg to 1 gm loss/day	2 to 3+ or 1 to 2 gm loss/day	4+ or 2 to 3.5 gm loss/day	Nephrotic syndrome or >3.5 gm loss/day
Hematuria	NA	NA	Microscopic only <10 RBC/hpf	Gross, no clots >10 RBC/hpf	Gross, with or without clots, or red blood cells casts	Obstructive or required transfusion

HPF=high powered field; RBC=red blood cells.

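### The SAP does not assure a within-participant count of new or worsening dipstick proteinuria, although protocol 9.3.4 promises a baseline-to-worst shift

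*SAP*

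**What the plan says.** **Risk.** Under renal effects, Protocol 2.3.1 states "Proteinuria was also observed in humans". The same row adds that trials to date have shown no clinical evidence of renal toxicity.

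**Collection.** In the Schedule of Activities (Protocol 1.3) the row "Hematology, chemistry, and urinalysis" is marked at Baseline, On-therapy and TOC. The urinalysis panel in Protocol 10.2 includes "pH, glucose, protein, blood, ketones, nitrite, and leukocyte esterase by dipstick". Study laboratory tests go to a central laboratory, "with the exception of dipstick urinalysis and urine pregnancy tests which will be performed locally".

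**Protocol analysis.** Protocol 9.3.4 says "The severity of specified AEs and laboratory abnormalities will be graded according to the modified DMID toxicity grading system". It also promises the frequency of laboratory abnormalities together with the shift from baseline to the worst post-baseline value, without excepting urinalysis. The toxicity table in Protocol 10.12 gives Grade 1 proteinuria as "1+ or 200 mg to 1 g loss/day". Grade 2 includes 2 to 3+ and Grade 3 includes 4+. Grade 4 has no dipstick value.

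**SAP analysis.** SAP 6.2.4.1 reprints the row (Grade 1: "1+ or 200 mg to 1 gm loss/day") but enters NA for both laboratory parameter and display label. It says that grading will use numerical criteria only. SAP 4.6.3.1 then has four relevant elements:
- a worst-case grade-increase table for tests gradable by DMID, with a missing baseline grade taken as grade 0;
- a worst-case change against normal range for tests not gradable by DMID;
- change-from-baseline tables for haematology and chemistry;
- for urinalysis, the sentence "Urinalysis results will be summarized using descriptive statistics".

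SAP 4.9, which lists changes from the protocol's analyses, mentions neither urinalysis nor DMID grading.

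**The concern.** Most rows mapped to NA in SAP 6.2.4.1 are tests outside the protocol's panel: fibrinogen, prothrombin time, APTT, methemoglobin, GGT, amylase, lipase and uric acid. Protein is different. It is measured at three visits, and it has an ordered dipstick scale printed beside the NA.

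Bladder infection can itself make a dipstick positive, so positivity may fall between Baseline and TOC as infection clears. In a table of categories by visit, that fall would be mixed with any new positives among women who were negative at Baseline. Only a comparison of each woman with her own baseline separates the two, and that is what protocol 9.3.4 promises. What is at stake is a descriptive safety output for a renal finding that the protocol itself names. The primary analysis is not affected.

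**Working it through.** The plan states no figure on this point, so there is nothing to reproduce. The check is a reading of the rules, followed by arithmetic on assumed rates.

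**1. Which SAP rule applies to dipstick protein?**

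| Reading of SAP 4.6.3.1 and 6.2.4.1 | Output for protein | What it shows |
|---|---|---|
| Gradable, because grades are printed | Worst-case grade increase | Full within-participant shift, but the NA mapping leaves no parameter to feed it |
| Not gradable, because the row is NA | Worst-case change against normal range | Increase to high, within participant |
| The urinalysis sentence stands alone | Number and percentage per category (SAP 4.1.1) | No within-participant comparison |

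The SAP does not choose between the second and third readings. The second also has limits. No normal range is stated for the locally read dipstick. If any positive result counts as high, a new 1+ and a new 4+ fall in the same cell, and a woman who goes from 1+ to 4+ is recorded as no change.

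**2. What can visit counts alone establish?**

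Let b be the proportion positive at Baseline and p the proportion positive at TOC. The proportion negative at Baseline and positive at TOC must lie between max(0, p − b) and min(1 − b, p). The planned gepotidacin number is 300 × 3/4 = 225. The values of b and p are assumptions.

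| b | p | New-onset proportion | Participants of 225 |
|---|---|---|---|
| 10% | 5% | 0% to 5% | 0 to 11 |
| 10% | 10% | 0% to 10% | 0 to 22 |
| 10% | 20% | 10% to 20% | 23 to 45 |
| 30% | 5% | 0% to 5% | 0 to 11 |
| 30% | 10% | 0% to 10% | 0 to 22 |
| 30% | 20% | 0% to 20% | 0 to 45 |

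With b = 50% the ranges equal those for 30%. The counts bound the number of new cases but do not identify it.

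**3. What would the two arms show side by side?**

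Assume 30% positive at Baseline, 90% of these cleared by TOC, and 5% of baseline-negative women newly positive on gepotidacin but none on nitrofurantoin.

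- Gepotidacin: 225 × 0.30 = 67.5 positive at Baseline, of whom 67.5 × 0.10 = 6.75 remain positive. New cases: 157.5 × 0.05 = 7.9. Positive at TOC: (6.75 + 7.875)/225 = 6.5%.
- Nitrofurantoin (300 × 1/4 = 75): 75 × 0.30 × 0.10 = 2.25 remain positive, and 2.25/75 = 3.0%.
- Difference between arms at TOC: 6.5% − 3.0% = 3.5 percentage points.

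If baseline positivity is 20% to 40% and new onset 3% to 10%, new cases range from 225 × 0.60 × 0.03 = 4 to 225 × 0.80 × 0.10 = 18. So the visit table by arm would show an excess on gepotidacin, but not how many women it represents as new cases or how severe they were.

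**The case against.** The strongest reply is that proteinuria is already captured by several routes.

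- **The rule for ungraded tests.** If NA means not gradable, the worst-case change against normal range applies on its face, with no urinalysis exception. This may be so, and it rules out saying that no output compares a woman with her baseline. The limits in step 1 remain.
- **Descriptive counts by arm.** SAP 4.1.1 defines categorical summaries as numbers and percentages, and the nitrofurantoin arm shows how far positivity falls as infection clears. A reader might infer that proteinuria goes uncounted, or that a harm would appear as an improvement. The documents do not support either, as step 3 shows.
- **Adverse events.** An abnormal urinalysis judged clinically significant is an adverse event (Protocol 10.3.1). It is then graded and tabulated, and it enters the screening in SAP 4.6.2.4. This stands in part. It depends on investigator judgement, and findings attributed to the underlying disease are excluded unless more severe than expected. In cystitis that attribution is easy to make.
- **Renal function.** Creatinine and urea are graded, and renal impairment is summarised. Neither measures protein.
- **The NA is deliberate.** Only numerical criteria are used, the grading is said to match the global studies, and haematuria is NA too. Protocol 9.3.4 also refers to specified abnormalities and to shift tables as appropriate. That explains the mapping, but it does not supply the baseline-to-worst shift promised in the same protocol section.
- **Confounding.** A positive dipstick at TOC may reflect persistent infection. This is true and belongs in the interpretation. It applies equally to the visit counts already planned.

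**Conclusion.** The point holds as a gap in specification. The SAP does not assure a within-participant count of new or worsening proteinuria, and it does not list this departure from protocol 9.3.4. The most favourable reading gives an increase-to-high count without grade and without worsening among women already positive. The least favourable gives visit counts only, which under the assumed rates of 30% and 10% are compatible with 0 to 22 new cases among 225.

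The size is modest. Visit counts by arm and adverse event reports capture part of any signal. A reader might also take proteinuria as established renal toxicity of gepotidacin, but Protocol 2.3.1 says no clinical evidence of renal toxicity has been seen.

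The conclusion about the rules rests on the documents alone. The numerical illustration rests on assumed positivity, clearance and onset rates, and on planned enrolment, whereas the Safety population will exclude undosed participants and one site. The case for acting is that the correction is cheap and the finding is one the protocol names.

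**What to change.** Either of two changes is enough.

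1. In SAP 6.2.4.1, replace NA in the Proteinuria row with the dipstick protein result, using the grades already printed (1+ as Grade 1, 2 to 3+ as Grade 2, 4+ as Grade 3). Include it by treatment group in the worst-case grade-increase table of SAP 4.6.3.1, and note it as an exception to the numerical-criteria rule.
2. Alternatively, state in SAP 4.6.3.1 that a shift table of dipstick protein category, from baseline to worst post-baseline, will be produced by arm.

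In both cases, show participants with a missing baseline dipstick separately. The present default of grade 0 would turn protein that was already there into an apparent increase. If neither change is adopted, record the departure from protocol 9.3.4 in SAP 4.9 and say whether the rule for ungraded tests covers urinalysis.

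The cost is a few lines of SAP text and one table row or one small table, from data already scheduled for collection. This assumes that the database holds the dipstick category and not only normal or abnormal, which the documents do not state. Because a positive result at TOC can reflect persistent infection, read the output against the nitrofurantoin arm and alongside microbiological outcome.
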